5.1.2 Exclusion criteria

1. Patients who have undergone systemic chemotherapy, radiotherapy, surgery, or hormone therapy < 2 weeks before enrollment, also see exclusion #8.

Note: Participants must have recovered from all AEs due to previous therapies to \leq Grade 1 or baseline. Participants with \leq Grade 2 neuropathy may be eligible.

Note: If participant received major surgery, they must have recovered adequately from the toxicity and/or complications from the intervention prior to starting study treatment.

2. Patients with a history of taking regorafenib or immune check point inhibitors.
3. Patients with hypertension that is difficult to control (systolic blood pressure ≥ 150 mmHg and diastolic blood pressure ≥ 90 mmHg) despite treatment with several hypotensive agents
4. Patients with acute coronary syndrome (including myocardial infarction and unstable angina), and with a history of coronary angioplasty or stent placement performed within 6 months before enrollment
5. Patients with a large amount of pleural effusion or ascites requiring more than weekly drainage.
6. Has a history of (non-infectious) pneumonitis that required steroids or has current pneumonitis.
7. Patients with a \geq grade 3 active infection according to NCI-CTCAE version 5.0
8. Patients with symptomatic brain metastasis (1-week washout is permitted for palliative radiation (≤ 2 weeks of radiotherapy) to non-CNS disease).
9. Patients with partial or complete gastrointestinal obstruction
10. Patients with interstitial lung disease with symptoms or signs of activity

11. Patients who test positive for either anti-HIV-1 antibodies, anti-HIV-2 antibodies, anti-HTLV-1 antibodies, hepatitis B surface antigen (HBsAg), or anti-hepatitis C virus (HCV) antibodies*. (please use prior history for reference, testing is not required unless deemed necessary by the investigator)

*Patients who test positive for either anti-HBs or anti-HBc antibodies, and those who have HBV-DNA measurements greater than the detection sensitivity will also be excluded.

12. Patients with concurrent autoimmune disease, or a history of chronic or recurrent autoimmune disease
13. Patients who require systemic corticosteroids (excluding temporary usage for tests, prophylactic administration for allergic reactions, or to alleviate swelling associated with radiotherapy) or immunosuppressants, or who have received such a therapy <14 days before enrollment in the present study
14. Patients with a history or findings of \geq grade III congestive heart failure according to the New York Heart Association functional classification
15. Patients with a seizure disorder who require pharmacotherapy
16. Persistent proteinuria > 3.5 g/24 hours measured by urine protein-creatinine ratio from a random urine sample (\geq Grade 3, NCI-CTCAE v 5.0).
17. Known hypersensitivity to any of the study drugs, study drug classes, or excipients in the formulation.
18. Major surgical procedure or significant traumatic injury within 28 days before start of study medication.
19. Non-healing wound, non-healing ulcer, or non-healing bone fracture
20. Patients with evidence or history of any bleeding diathesis, irrespective of severity
21. Any hemorrhage or bleeding event \geq CTCAE Grade 3 within 4 weeks prior to the start of study medication
22. Women who are pregnant or breastfeeding, or with the potential for pregnancy unwilling to undergo contraception.
23. Has a diagnosis of immunodeficiency or is receiving chronic systemic steroid therapy (in dosing exceeding 10 mg daily of prednisone equivalent) or any other form of immunosuppressive therapy within 7 days prior to the first dose of study drug.
24. Has an active infection requiring systemic therapy.
25. MSI colorectal cancers are not candidate for enrollment on this trial.

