- Alpha hydroxyl acids (AHA) based creams may be applied liberally 2 times a day. Approximately 5% to 8% provides gentle chemical exfoliation.
- Topical analgesics (e.g. lidocaine 2%) are to be considered for pain control.
- Topical corticosteroids like clobetasol 0.05% should be considered for subjects with Grade 2 or 3 HFSR. Avoid systemic steroids.

Tender areas should be protected as follows:

- Use socks/gloves to cover moisturizing creams
- Wear well-padded footwear
- Use insole cushions or inserts (e.g. silicon, gel)
- Foot soaks with tepid water and Epson salts

Hypertension

Hypertension is a known AE associated with regorafenib treatment. Subject will have their blood pressure measured at least weekly at the study site during the first 6 weeks of treatment. If additional blood pressure measurements are done outside the study site, and the blood pressure is > 140 mm Hg systolic or > 90 mm Hg diastolic (NCI CTCAE v5.0), then the subject must contact study personnel. The management of hypertension, including the choice of antihypertensive medication, will be performed according to local standards and to the usual practice of the investigator. Every effort should be made to control blood pressure by medical means other than study drug dose modification. If necessary, Table 6-4 outlines suggested dose reductions.

Table 6-4: Management of Treatment-Emergent Hypertension

Grade (CTCAE v5.0)	Antihypertensive Therapy	Regorafenib Dosing
1 Prehypertension (systolic BP 120 - 139 mmHg or diastolic BP 80 - 89 mmHg)	None	
 Continue regorafenib Consider increasing blood pressure (BP) monitoring
2 Systolic BP 140 - 159 mmHg or diastolic BP 90 - 99 mmHg, OR Symptomatic increase by > 20 mmHg (diastolic) if previously within normal limits	Treat with the aim to achieve diastolic BP ≤ 90 mm Hg: If BP previously within normal limits, start anti-hypertensive monotherapy If patient already on anti-hypertensive medication, titrate up the dose.	
 Continue regorafenib If symptomatic, hold regorafenib until symptoms resolve AND diastolic BP ≤ 90 mm Hg^a. When regorafenib is restarted, continue at the same dose level.

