3 Systolic BP ≥ 160 mmHg or diastolic BP ≥ 100 mmHg OR More than one drug or more intensive therapy than previously used indicated	Treat with the aim to achieve diastolic BP ≤ 90 mm Hg: Start anti-hypertensive medication AND/OR Increase current anti-hypertensive medication AND/OR Add additional anti-hypertensive medications.	
 Hold regorafenib until diastolic BP ≤ 90 mm Hg, and if symptomatic, until symptoms resolve.^a When regorafenib is restarted, continue at the same dose level. If BP is not controlled with the addition of new or more intensive therapy, reduce by 1 dose level.^b If Grade 3 hypertension recurs despite dose reduction and antihypertensive therapy, discontinue therapy
4 Life-threatening consequences (eg, malignant hypertension, transient or permanent neurologic deficit, hypertensive crisis)	Per institutional guidelines	Discontinue therapy

a. Patients requiring a delay of >4 weeks should go off protocol therapy
 
b. If BP remains controlled for at least one cycle, dose re-escalation permitted per investigator's discretion.
 
c. Patients requiring >1 dose reductions should go off protocol therapy. If reduction required resulting in a dose of less than 80mg q.o.d of regorafenib, then regorafenib will be permanently discontinued.
		

Liver Function Abnormalities

For patients with observed worsening of serum liver tests considered related to regorafenib (i.e. where no alternative cause is evident, such as post-hepatic cholestasis or disease progression), the dose modification and monitoring advice in Table 6-5 should be followed.

Regorafenib is a UGT1A1 inhibitor. Mild, indirect (unconjugated) hyperbilirubinemia may occur in patients with Gilbert's syndrome.

Table 6.5: Dose Modification/interruption for LIVER toxicity

General instructions:

If any of below outlined events will occur: Monitor liver function tests weekly or more frequently until recovery to baseline or stabilization.

If reduction required resulting in a dose of less than 80mg qod of regorafenib, then regorafenib will be permanently discontinued.

For any G3/4 increases in ALT/AST or bilirubin:

If the increases are primarily seen under ongoing regorafenib treatment (e.g. last pembrolizumab infusion was given one week before):

Closely monitor for potential de-challenge, i.e. whether a decrease in ALT/AST and/or bilirubin values is seen within 3 days of regorafenib interruption.

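### Exclusion 3 requires both blood pressure limits at once, so isolated elevation on several agents is not excluded, and exclusion 4 is ambiguous about acute coronary syndrome and its 6-month window

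*Combined protocol and SAP*

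**What the plan says.** Section 5.1.2, exclusion 3, defines uncontrolled hypertension by two limits: "Patients with hypertension that is difficult to control (systolic blood pressure ≥ 150 mmHg and diastolic blood pressure ≥ 90 mmHg". A treatment condition follows: the pressure must be at this level although the patient takes several antihypertensive drugs. Exclusion 4 reads "Patients with acute coronary syndrome (including myocardial infarction and unstable angina), and with a history of coronary angioplasty or stent placement". The sentence ends with a time limit of 6 months, stated next to the procedure. The synopsis carries both criteria in the same words, so it does not settle either one.

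The only other cardiac exclusion is number 14, which concerns "congestive heart failure according to the New York Heart Association functional classification" at grade III or worse.

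On study, the Hypertension text in section 6.3.1 states "Hypertension is a known AE associated with regorafenib treatment". It tells the patient to contact staff when a reading taken away from the site shows that "the blood pressure is > 140 mm Hg systolic or > 90 mm Hg diastolic". Table 6-4 gives the numerical part of Grade 3 as "Systolic BP ≥ 160 mmHg or diastolic BP ≥ 100 mmHg".

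**The concern.** An exclusion built with *and* applies only when every part is true. In exclusion 3 this leaves out a patient whose systolic pressure stays high on several agents while the diastolic is below 90, and likewise a patient with only the diastolic raised. The protocol itself recognises hypertension as a risk of regorafenib, and elsewhere it acts when either component is high.

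Exclusion 4 can be read in two ways that admit different patients, and one of them lets in a patient shortly after an infarction.

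The stake is mainly patient safety. The second is consistency: section 3 foresees one or two further institutions, and under section 11.2.2 each site checks eligibility first and submits a signed checklist for central verification. Sites that read the same sentence differently would enrol different patients.

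**Working it through.** No sample size, power or error rate is involved. The check is of the logic of each criterion, followed by a search for another criterion that would cover the gap.

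**Exclusion 3.** Inputs: limits of 150 and 90 (section 5.1.2); contact rule above 140 or above 90 (section 6.3.1, Hypertension); numerical Grade 3 at 160 or 100 (Table 6-4). Every patient below is taken to be on several agents.

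| Reading | Systolic ≥ 150 | Diastolic ≥ 90 | Exclusion 3 as written | Contact rule | Table 6-4 Grade 3, numerical |
|---|---|---|---|---|---|
| 150/90 | yes | yes | excluded | met (150 > 140) | not met |
| 178/86 | yes | no | not excluded | met (178 > 140) | met (178 ≥ 160) |
| 145/95 | no | yes | not excluded | met (145 > 140) | not met |

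So a patient exactly at the two limits is kept out, while one whose systolic pressure is 178 − 150 = 28 mmHg higher is not, because the diastolic is 90 − 86 = 4 mmHg below its limit. With the same limits joined by *or*, all three are excluded.

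**Exclusion 4.** Let A be acute coronary syndrome and B be angioplasty or stent within 6 months.

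| Patient | A | B | Literal (A and B) | List (A or B) |
|---|---|---|---|---|
| Infarction 3 weeks ago, managed medically | yes | no | not excluded | excluded |
| Recent elective stent, no acute coronary syndrome | no | yes | not excluded | excluded |
| Infarction more than 6 months ago, no procedure | yes, if no time limit applies to A | no | not excluded | excluded only if the window does not govern A |

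The first two rows turn on the conjunction, the third on the reach of the window. The sentence settles neither.

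**Search for cover.** The inclusion list (5.1.1), the exclusion list (5.1.2), the excluded therapies (5.1.3) and the synopsis contain no other criterion on blood pressure or coronary events. Exclusion 14 concerns heart failure only. There is no general investigator-judgement exclusion; the provision on harm to the subject in section 5.2.1 concerns withdrawal after entry. Section 7 schedules vital signs and an ECG at screening, but no eligibility rule uses the result.

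**The case against.** *The two criteria are not equally faulty.* This stands. A reader might infer that exclusion 4 plainly admits recent infarctions. The comma and the repeated *with* permit a list reading, which was probably intended and under which acute coronary syndrome already excludes. Against that, the footnote to exclusion 11 marks its second group explicitly with *those*, and exclusion 4 does not. Ambiguity is what the text supports.

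*The window could simply be applied to both conditions.* The documents do not support that choice. On the list reading, acute coronary syndrome may carry no time limit, so adding one could loosen the criterion. It is also a clinical decision for the sponsor.

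*Table 6-4 does not contradict exclusion 3.* Correct in the strict sense. The table grades hypertension arising on treatment, the contact rule is a prompt to call the site, and exclusion 3 describes hypertension resistant to several agents. Grade 3 can also be met through a need for more intensive therapy. An *or* in those places does not oblige the entry rule to use one. What remains is an inconsistent construction, with an outcome (150/90 out, 178/86 in) that is hard to defend.

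*The gap is narrow.* This also stands. A reader might infer that any systolic value is admissible through the conjunction alone. The criterion also requires several agents, so the conjunction matters only for patients already on them. Changing *and* to *or* does not reach a patient with the same reading on one drug or none.

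*Safety data would hardly be distorted.* Largely right. Under section 7.3.1.1, a condition present before consent and unchanged in intensity is medical history; only worsening counts as an adverse event. Blood pressure is measured at least weekly for the first 6 weeks. These provisions limit the consequence but do not replace an entry criterion.

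**Conclusion.** The point holds as a drafting fault with a safety consequence. For exclusion 3 it is firm: as written, in both section 5.1.2 and the synopsis, a patient on several agents with only one component above its limit is not excluded, and nothing else in the eligibility list covers that patient. For exclusion 4 the supportable conclusion is that the conjunction and the reach of the 6-month window are both unclear.

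The size cannot be put in patients. The documents do not say how many candidates would have isolated elevation on several agents or a recent medically managed infarction. A reader might turn to the 7% rate of Grade 3 or higher hypertension reported for CORRECT (section 1.4.2). It does not serve here: it counts events on treatment, not patients at entry, and CORRECT gave 160 mg for three weeks of four, whereas section 6.1 lists 80 mg and 120 mg on days 1–14 of 21.

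The primary endpoint definition, sample size, power and type I error are unaffected. The conclusion assumes that sites apply the criteria as worded; many investigators would probably screen such patients out on their own judgement.

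**What to change.** - **Exclusion 3:** reconcile it with the either-component construction in the Hypertension text and Table 6-4, keeping the stated limits and the condition on several agents. If both limits together are truly meant, say so and give the reason.
- **Exclusion 4:** reword it to state whether acute coronary syndrome and angioplasty or stent each exclude on their own, and which of them the 6-month window governs. The sponsor should decide both.
- **Elsewhere:** make the same edits in the synopsis and in the eligibility checklist and worksheet used under section 11.2.2.

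The cost is a wording amendment, a checklist update and possibly a few more screen failures. The gain is patient safety and uniform application across sites. No statistical quantity changes.

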5.1.3 Excluded therapies and medications, previous and concomitant

- Concurrent anti-cancer therapy (chemotherapy, radiation therapy, surgery, immunotherapy, biologic therapy, or tumor embolization) other than study treatment (regorafenib and pembrolizumab).
- Concurrent use of another investigational drug or device therapy (i.e., outside of study treatment) during, or within 2 weeks of trial entry (signing of the informed consent form is OK in the washout period).

- Major surgical procedure, open biopsy, or significant traumatic injury within 28 days before start of study medication.
- Therapeutic anticoagulation with Vitamin-K antagonists (e.g., warfarin) or with heparins and heparinoids. However, prophylactic anticoagulation as described below is allowed:
 - Low dose warfarin (1 mg orally, once daily) with PT-INR $\leq 1.5 \times$ ULN is permitted. Infrequent bleeding or elevations in PT-INR have been reported in some subjects taking warfarin while on regorafenib therapy. Therefore, subjects taking concomitant warfarin should be monitored regularly for changes in PT, PT-INR or clinical bleeding episodes.
 - Low dose aspirin (≤ 100 mg daily).
 - Prophylactic doses of heparin.
- During the study, strong CYP3A4 inhibitors (eg, clarithromycin, grapefruit juice, indinavir, itraconazole, ketoconazole, nefazodone, nelfinavir, posaconazole, ritonavir, saquinavir, telithromycin, voriconazole) or strong CYP3A4 inducers (eg, carbamazepine, phenobarbital, phenytoin, rifampin, St. John's Wort) are not permitted.
- Live vaccines administered <30 days before the initiation of treatment with the investigational drug and during the trial period. Examples of live vaccines are as follows (however, the list is not exhaustive): measles, mumps, rubella, chicken pox/herpes zoster, yellow fever, rabies*, BCG for tuberculosis, and typhoid vaccines*. Inoculation with inactive vaccines (e.g., seasonal influenza vaccines) is permitted; however, the intranasal administration of attenuated influenza vaccines (e.g., Flu-Mist®) is prohibited.
- Systemic glucocorticoids for purposes other than treating symptoms caused by notable events with a suspected immunological etiology. Upon deliberation with the PI, the use of corticosteroids may be permitted according to the physiological dose required to alleviate symptoms (e.g., to control symptoms of acute asthma).

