5.1 Eligibility

5.1.1 Inclusion criteria

1. Patients who provided written informed consent to be subjects in this trial
2. Patients at least 18 years of age on the day of providing consent
3. Patients with histologically or cytologically confirmed advanced or metastatic colorectal cancer who had failed or are intolerant of oxaliplatin, irinotecan, and 5-FU. Patients with MSI colorectal cancer are not candidate for treatment on this trial.
4. Patients with an Eastern Cooperative Oncology Group (ECOG) performance status (PS) of 0 or 1 within 7 days of start of treatment
5. Patients capable of taking oral medication
6. Patients with evaluable or measurable lesions as per RECIST version 1.1
7. Patients with adequate organ function at the time of enrollment as defined below:
 - Neutrophil count $\geq 1200/\text{mm}^3$
 - Platelet count $\geq 7.5 \times 10^4/\text{mm}^3$
 - Hgb $> 9.0\text{g/dL}$ (transfusion > 2 weeks before testing permitted)
 - Aspartate transaminase (AST), alanine transaminase (ALT) ≤ 2.5 -times the upper limit of normal (≤ 5 -times in patients with liver metastasis)
Total bilirubin ≤ 1.5 -times the upper limit of normal
 - Creatinine ≤ 1.5 -times the upper limit of normal
 - Lipase $\leq 1.5 \times$ the ULN
 - International normalized ratio (INR) $\leq 1.5 \times$ ULN and partial thromboplastin time (PTT) or activated partial thromboplastin time (aPTT) $\leq 1.5 \times$ ULN unless receiving treatment with therapeutic anticoagulation. Patients being treated with anticoagulant, e.g. heparin, will be allowed to participate provided no prior evidence of an underlying abnormality in these parameters exists. Close monitoring of at least weekly evaluations will be

performed until INR and PTT are stable based on a pre-dose measurement as defined by the local standard of care.

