- Subjects who are therapeutically treated with an agent such as warfarin or heparin will be allowed to participate provided that their medication dose and INR/PTT are stable. Close monitoring (day 5 of cycle 1 and day 1 of each cycle) is mandatory. If either of these values are above the therapeutic range, the doses should be modified and the assessments should be repeated weekly until they are stable.

The following are not permitted:

- Other investigational treatment during or within 2 weeks before starting study treatment
- Systemic antitumor therapy, including cytotoxic therapy, signal transduction inhibitors, immunotherapy, and hormonal therapy
- Bone marrow transplant or stem cell rescue
- Subjects taking narrow therapeutic index medications should be monitored proactively (e.g. warfarin, phenytoin, quinidine, carbamazepine, Phenobarbital, cyclosporin, and digoxin). Warfarin is metabolized by the cytochrome enzyme CYP2C9 and its levels may be especially affected by regorafenib
- Use of any herbal remedy (e.g. St. John's wort [*Hypericum perforatum*])
- Please note: Patients should be seen frequently / early during treatment as per Prescribing Information
- Liver function tests should be obtained before initiation of regorafenib and monitored at least every 2 weeks during first 2 months of treatment. Thereafter liver function should be monitored monthly or more frequently as clinically indicated
- Monitor blood pressure weekly for the first 6 weeks of treatment and every cycle or more frequently as clinically indicated.

7. Timing of assessments

Potential candidates will undergo screening as outlined in calendar, **study treatment has to be started within 7 days of screening.**

All subjects will be seen weekly for the first two cycles and every 3 weeks afterwards (coordinated with days of pembrolizumab administration). Tumor measurement should be done every 8 weeks.

Each cycle can be started within 5 days of expected dates to accommodate for scheduling issues.

	Screening	Cycle 1 and 2			Cycle 3 on			Follow-up	
		Day 1	Day 8	Day 15	Day 1	Day 8	Day 15	End of TX 30 days (+/- 7 days) of last tx date	FU phone call every 6 months (+/- 7 days) for 24 months
Informed consent, Review of Eligibility Criteria	X ²								
Medical History & Demographics	X ²								
Physical Exam (including vital signs), Weight, Performance Status	X ²	X	X	X	X			X	
Tumor biopsy (optional and encouraged)				X*					
PT/INR, PTT, aPTT	X ²		X	X*					

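### Section 5.1.3 excludes therapeutic warfarin and heparins that inclusion criterion 7 and section 6.6 conditionally allow, and the INR/PTT monitoring texts do not match

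*Combined protocol and SAP*

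**What the plan says.** Section 5.1.3 covers therapies excluded both before and during the study. It lists "Therapeutic anticoagulation with Vitamin-K antagonists (e.g., warfarin) or with heparins and heparinoids". The exception follows at once: "However, prophylactic anticoagulation as described below is allowed". For warfarin the exception reads "Low dose warfarin (1 mg orally, once daily) with PT-INR" at most 1.5 × ULN. Low-dose aspirin and prophylactic heparin are the other two items.

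Inclusion criterion 7 in section 5.1.1 sets INR and PTT/aPTT limits of 1.5 × ULN "unless receiving treatment with therapeutic anticoagulation". It continues: "Patients being treated with anticoagulant, e.g. heparin, will be allowed to participate provided no prior evidence of an underlying abnormality in these parameters exists". It then asks for INR/PTT checks at least weekly until the values are stable. The synopsis repeats this criterion.

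Section 6.6, in its list of permitted concomitant therapy, says: "Subjects who are therapeutically treated with an agent such as warfarin or heparin will be allowed to participate". The same sentence makes this conditional on a stable dose and stable coagulation values. The section makes checks mandatory on cycle 1 day 5 and on the first day of every cycle, with weekly repeats if a value is above the therapeutic range.

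The study calendar in section 7, as extracted, shows coagulation tests at screening, day 8 and day 15. The day 15 entry is tied by footnote to the optional biopsy.

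**The concern.** Eligibility text should give one answer for one patient. Here, one section forbids a co-medication that two others allow under conditions. A patient enrolled under criterion 7 and section 6.6 can be recorded as a protocol violation under 5.1.3. A patient turned away under 5.1.3 could have been accepted under the other two. Section 13.1 requires strict adherence to everything the protocol specifies, and that is not possible for such a patient.

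The co-medication also has a safety aspect that the protocol itself recognises. Section 5.1.3 notes that bleeding or raised PT-INR has been seen infrequently in subjects taking warfarin with regorafenib. Section 6.6 warns that regorafenib may particularly affect warfarin levels. If the permissive reading applies, the INR/PTT checks become part of the condition for taking part, so they need to be the same wherever they are described.

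**Working it through.** There is no figure to reproduce; the check is a comparison of texts.

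| Place | Therapeutic warfarin or heparin | Condition | INR/PTT checks |
|---|---|---|---|
| 5.1.3 | Excluded | Prophylactic use only | Regular monitoring for subjects on concomitant warfarin |
| 5.1.1 no. 7 and synopsis | Limits waived; anticoagulated patients admitted | No prior underlying abnormality | At least weekly until stable |
| 6.6 | Allowed | Stable dose and stable INR/PTT | Cycle 1 day 5, first day of every cycle; weekly if above range |
| Calendar, section 7 | Not addressed | None | Screening, day 8, day 15 (biopsy) |

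**Test case.** Take a patient on a stable therapeutic dose of warfarin or heparin, with stable INR/PTT and no prior underlying coagulation abnormality.

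1. Under criterion 7, the INR/PTT limits do not apply and the abnormality condition is met. The patient may enter.
2. Under 6.6, the dose and the values are stable. The patient may take part.
3. Under 5.1.3, the therapy is on the excluded list. The prophylactic exception does not help, because the treatment is therapeutic; for warfarin it stops at 1 mg daily with PT-INR no higher than 1.5 × ULN.

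No reading satisfies all three.

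**Is there a tie-breaker?** The numbered exclusion criteria in 5.1.2 do not mention anticoagulants, and no sentence gives one section precedence. A later bullet in 6.6 names warfarin under the heading for what is not permitted, but its content is an instruction to monitor, so it does not settle the matter.

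**Monitoring.** Criterion 7 foresees weekly checks until stability is reached, whereas 6.6 makes stability a condition of taking part and then fixes particular days. A site could perform both sets of tests. The calendar, however, has no coagulation test on cycle 1 day 5 or on the first day of any cycle, so a site working from the calendar would miss the checks that 6.6 calls mandatory.

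**The case against.** The strongest defence concerns reach and consequence; the contradiction itself is plain.

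- **Scope.** A reader might infer that every anticoagulated patient is caught. The text does not support that. Section 5.1.3 names only vitamin-K antagonists, heparins and heparinoids, so no conflict is shown for other classes. The permissions are also conditional, and a patient who fails the conditions is not clearly eligible anywhere.
- **Divergence between sites.** A reader might infer that sites are certain to decide differently. Section 10 calls the trial single-institution, section 3 foresees only one or two more sites, and section 11.2 routes eligibility through central verification before registration. That limits divergence in enrolment, but the central checker works from the same contradictory text. Decisions may differ; it is not established that they will.
- **Safety.** The bleeding remark in 5.1.3 describes infrequent events, sits in the bullet that permits low-dose warfarin, and leads to monitoring. It is not given as the reason for the exclusion. The permissive sections require monitoring too, and exclusions 20 and 21 in 5.1.2 separately bar a bleeding diathesis and a recent bleed of grade 3 or higher. The documents do not support saying that these patients go unmonitored.
- **Placement.** Section 5.1.3 is not part of the numbered exclusion list. Its heading nevertheless covers previous and concomitant therapy, so it bears on entry as well as on treatment during the study.

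The first three points narrow the claim. None of the four removes the contradiction.

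**Conclusion.** The contradiction stands for patients on an agent named in 5.1.3 who meet the conditions in criterion 7 and section 6.6. They are both eligible and on an excluded therapy. The mismatch in INR/PTT monitoring is a second, linked inconsistency. Its calendar part rests on the table as extracted from the PDF and should be checked against the original layout.

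The number of patients is unknown. A reader might be tempted to apply an assumed share to the phase II sample: 5% to 15% of 63 is 0.05 × 63 = 3.15 to 0.15 × 63 = 9.45, or about 3 to 9 patients. The documents give no basis for that share. It would also count patients on anticoagulants that 5.1.3 does not name, and the denominator is itself unsettled (69 in the synopsis row on number of subjects, 63 in section 10.1). No count should be reported.

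This is an internal contradiction in an eligibility and co-medication rule, not a questionable design choice. It leaves the sample size, the error rates and the PFS analysis unchanged. It merits correction because the plan cannot be followed as written for these patients.

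**What to change.** In one amendment, reconcile the synopsis, 5.1.1 no. 7, 5.1.3, 6.6 and the study calendar so that they contain:

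1. a single statement on whether therapeutic anticoagulation is permitted, naming the agents covered and any conditions; and
2. a single INR/PTT monitoring schedule that matches that statement and appears in the calendar.

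Delete the conflicting text, and bring the eligibility checklist used for registration into line. The sponsor and the investigator must decide which clinical rule applies; this review takes no position on it.

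The cost is protocol wording and its approval. If the exclusion is kept, the eligible pool shrinks by an amount the documents do not allow us to estimate. If the permission is kept, the calendar must carry the tests that go with it. Neither choice requires a change to the statistical section.
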